2. LVEF <50%
3. Liver dysfunction (AST, ALT, total bilirubin, or alkaline phosphatase level greater than two times the normal range)
4. Clinical evidence of liver disease (enlarged liver, caput medusa, spider angiomas, or other signs of liver disease on exam)
5. Pregnancy
6. Inability to give informed consent
7. Taking or have taken amiodarone within one month prior to procedure
8. Taking or have taken dofetilide within 24 hours prior to the procedure
9. General severe intolerance to alcohol

## 3.0 STUDY TREATMENT

Demographic and medical history information will be obtained by chart review and by questionnaire administered by a member of the research team. Prior to the procedure, patients will be instructed to abstain from alcohol for 48 hours and to stop antiarrhythmic drugs for at least 5 half-lives. Per the standard AF ablation procedure with a double transseptal puncture, catheters will be positioned. Study coordinators measure conduction times using electronic

calipers and custom software in regular use in the UCSF EP laboratory, and EP measurements are then reviewed offline by the PI blinded to treatment assignment.

### **3.1 Anesthesia Protocol**

To minimize the effects of anesthetic agents on AERP and conduction time (see Operations Manual), the anesthesia team will follow a specific anesthesia protocol for HOLIDAY, devised in collaboration with the Anesthesia Department at UCSF, from induction to termination of the study protocol. Propofol, remifentanyl and nitrous oxide may be used at induction, with cis-atracurium for paralysis. Prior to transseptal access, nitrous oxide and cis-atracurium should be turned off, though propofol and remifentanyl infusions can continue. From transseptal access through the end of the experimental portion of the procedure, only a propofol infusion may be used. If remifentanyl is necessary after transseptal access, the anesthesia team may also use remifentanyl so long as remifentanyl is also infused for the remainder of the experimental portion of the procedure to ensure consistency. Phenylephrine may be titrated throughout the procedure to maintain a mean arterial pressure above 70 mmHg.

The following medications may not be used until after completion of the experimental portion: benzodiazepines, fentanyl, rocuronium, succinylcholine, ketamine, scopolamine, and inhaled anesthetics other than nitrous oxide. Only in the case of an emergency, may anticholinergics be used.

### **3.2 Catheter Placement**

Following the initiation of sedation, intra-cardiac multipolar electrocatheters will be placed in the following positions under fluoroscopic guidance: decapolar catheter in the coronary sinus (CS), decapolar catheter along the crista terminalis, quadripolar catheter along the medial tricuspid annulus at the position of the His bundle, duodecapolar circular catheter in the left upper pulmonary vein, and quadripolar ablation catheter in the right upper pulmonary vein. If the ablation procedure were a cryoballoon PVI, four, instead of five, catheters will be used: decapolar catheter in the coronary sinus (CS), decapolar catheter along the crista terminalis, quadripolar catheter along the medial tricuspid annulus at the position of the His bundle, and cryoballoon catheter in the left upper pulmonary vein. (See Operations Manual for details)

Catheter repositioning should be avoided to prevent disrupting post-procedure conduction time measurements. Prior to transseptal access, the alcohol or placebo solution will be connected to minimize left atrial time.

### **3.3 Pre-Infusion EP Study**

Immediately following catheter placement, a one-minute premature atrial contraction (PAC) count will be conducted. AERP measurements will then be taken at the following bipoles: CS proximal, CS distal, high right atrium (crista terminalis catheter), left upper pulmonary vein, and right upper pulmonary vein. The AERP will be obtained by an incremental technique using a 600 ms drive cycle length for 8 beats (S1) at twice pacing threshold with incremental steps for the atrial extrastimuli (S2). The first drive train at each location should begin with an atrial extrastimuli (S2) of 140 ms, which is not expected to result in atrial capture. Once the first atrial capture is achieved, the S2 will be decreased by 5 ms. AERP will be defined as the longest S1-S2 interval that fails to result in atrial capture. (See Operations Manual for details)

### 3.4 Infusion

After the first EP study, the intravenous ethanol or placebo infusion will be initiated while the left atrial anatomic map is being constructed to reduce time added to the ablation procedure and minimize risk. The infusion is run by an iMED Gemini PC-2TX pump connected to and controlled by the CAIS 2.0 computer software. The ethanol infusion will consist of a 6% volume/volume ethanol solution in 0.45% saline titrated by the BrAC quick clamp method until a steady state is achieved at a blood alcohol concentration of 0.08%. The mean time to achieving this steady state is regulated by the CAIS 2.0 software to be approximately 20 minutes. Infusion rates are determined by the patient's height, weight, age, and sex, but are automatically adjusted depending on the patient's breath alcohol measurements, which are taken every three to four minutes until steady state is reached.

Patients assigned to the placebo group will receive 5% dextrose (D5) in 0.45% saline. BrAC measurements will be obtained at identical intervals for all participants; BrAC measurements will be randomly generated within two standard deviations of the predicted values calculated by the CAIS 2.0 software based on height, weight, age, and sex. The randomly generated BrAC values will be input into the CAIS 2.0 software, as for patients receiving an alcohol infusion, and the infusion rates will be automatically adjusted accordingly.

Once the BrAC reading is  $\pm 0.002\%$  from 0.080% (steady state), BrAC measurements will be taken every 10 minutes and input into the CAIS 2.0 software. Breath alcohol measurements will be taken using the Intoximeters Alco Sensor IV fitted with a one-way valve adaptor for intubated patients. (See Operations Manual for details)

### 3.5 Post-Infusion EP Study

As soon as the blood alcohol content reaches a steady state of  $0.080\% \pm 0.002\%$ , a one-minute premature atrial contraction (PAC) count will be conducted. AERP measurements will then be taken at the following bipoles: CS proximal, CS distal, high right atrium (crista terminalis catheter), left upper pulmonary vein, and right upper pulmonary vein. The AERP will be obtained by an incremental technique using a 600 ms drive cycle length for 8 beats (S1) at twice pacing threshold with incremental steps for the atrial extrastimuli (S2). The first drive train at each location should begin with an atrial extrastimuli (S2) of 140 ms, which is not expected to result in atrial capture. Once the first atrial capture is achieved, the S2 will be decreased by 5 ms. AERP will be defined as the longest S1-S2 interval that fails to result in atrial capture. (See Operations Manual for details)

Following the PAC count and AERP measurements, a phenylephrine infusion will be started prior to the initiation of the isoproterenol infusion to maintain a mean arterial pressure of  $>60$  mmHg. Isoproterenol hydrochloride will then be infused at the following rates for 2 minutes each: 3 mcg/min, 6 mcg/min, 12 mcg/min, and 20 mcg/min. If AF or another arrhythmia initiates at any point during the isoproterenol infusion and is sustained over 30 seconds, the isoproterenol infusion will be stopped, the rhythm documented, and the study terminated.

If neither AF nor another arrhythmia lasting over 30 seconds occurs after 2 minutes of 20 mcg/min isoproterenol infusion, the isoproterenol infusion will be stopped. Once the heart rate falls below 100 bpm, up to 3 bursts of rapid atrial pacing will be performed from the CS proximal bipole. If AF or another arrhythmia initiates at any point during the burst pacing and is sustained over 30 seconds, the study will be terminated and the rhythm documented.

### **3.6 Assessment of Study Treatment Completion**

At the Baseline Visit, upon completion of the study treatment, the Investigator will complete the Study Treatment CRF. The Investigator will record details from the study treatment procedure (e.g., pre-procedure medications, details regarding pericardial and transseptal access, and fluoroscopy time) and will indicate whether the study procedure was completed as intended.

## **4.0 PARTICIPANT EARLY TERMINATION**

Full details regarding procedures for early termination will be outlined in the Operations Manual.

### **4.1 Untreated Randomized Participants**

After randomization, if an exclusionary criterion is identified prior to or at the start of the study procedure, the participant will not undergo the study infusion procedure. Randomized participants may be early terminated, prior to commencing the study procedure, and will not receive the study infusion if any of the following study exclusions are identified:

- Participants who present in AF sustained >1 week
- If a participant does not present in sinus rhythm at the procedure, but he or she has proven to be in sinus rhythm at the enrollment visit, it is up to the attending whether or not to cardiovert the patient and proceed with study protocol. If the participant is to be cardioverted, the cardioversion should take place prior to transseptal puncture and following right catheter placement to minimize potential effects on AERP and conduction times. If a second AF episode initiates and is sustained over 2 minutes prior to initiation of study procedure, the study will be aborted.

These participants will be considered as “Untreated Participants”. Unrandomized participants who do not commence/receive the study infusion will not continue in follow-up and will not be included in analyses.

### **4.2 Unsuccessfully Treated Participants**

After enrollment, if the study infusion commenced and was stopped and/or determined by the study Principal Investigator to be unsuccessful (i.e., immediately after the procedure, the investigator determines that the protocol was not completely executed) for any reason, the participant will continue in follow-up.

#### **4.2.1 Early Stopping of Study Infusion Protocol ONLY**

If the study infusion commenced and the participant develops AF that is sustained over 2 minutes during study procedure (excluding the AF susceptibility testing section), the patient should be cardioverted to sinus rhythm, at the discretion of his or her attending physician. If a second AF episode initiates and is sustained over 2 minutes, the study will be stopped. If a participant develops a non-AF tachyarrhythmia that persists over 2 minutes, it will be up to the attending physician to map and/or ablate the rhythms.

If the study infusion (ethanol or placebo) protocol commenced prior to AF development, the participant will not be early terminated and will continue in follow-up. These participants will be considered as “Unsuccessfully Treated Participants”.

### 4.3 Participant Withdrawals

Each participant will be informed that participation in the study is voluntary and that he or she may withdraw from the study at any time without effect on subsequent medical treatment or relationship with the treating physician. Participants who discontinue follow-up at any time after study treatment will be included in analyses.

### 4.4 Other Early Terminations

Participants who discontinue follow-up at any time after study treatment will be included in analyses.

Lost to Follow-Up: If a participant fails to return for at least one follow up visit (3, 6, and 12 months post-procedure) and cannot be reached by phone within the visit windows, the participant will be designated an early termination. The study personnel will show "due diligence" by documenting in the source documents, all steps taken to contact the participant, e.g., dates of telephone calls, registered letters, etc. Vital status for participants lost to follow-up may be later obtained using outside records/death registries.

Principal Investigator Determination: Participants should also be early terminated at any time if the Principal Investigator concludes that it would be in the participant's best interest for any reason. Protocol deviations should not lead to early termination unless they indicate a significant risk to the participant's safety.

## 5.0 STUDY PROCEDURES

Table 2 provides an overview of the evaluations to be performed at each of the study visits. Full details regarding the all study measurements and timing of data collection will be outlined in the Operations Manual.

**Table 2. Schedule of Evaluations and Visits**

	Screening	Baseline Study Infusion	Follow-Up Visits		
			Month 3	Month 6	Month 12/ Close-Out
Informed consent	x				
Inclusion/ Exclusion Evaluation	x				
Other laboratory evaluations	x				
Medical History	x				
Echo (TTE)*	x 				
Height	x				
Weight	x				
ECG	x	x			
Vital signs		x			
Concomitant Medications		x	x	x	x
Targeted Adverse Events		x	x	x	x
Serious Unexpected Adverse Events		x	x	x	x

Collection of materials for Targeted AEs/SAEs (if applicable)		X	X	X	X
Targeted medical care utilization (e.g., cardiac care during follow-up)			X	X	X

† Must be performed  $\geq 1$  year prior to study procedure

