### 5.1 Screening for Inclusion/Exclusion Criteria & Randomization

Each potential participant's medical record will be reviewed for available inclusion and exclusion criteria data. After the participant provides informed consent, his or her medical history and additional demographic data will be obtained. Initial screening will occur at least 1 day prior to the patient's scheduled ablation procedure.

The pharmacy that prepares the ethanol/placebo infusion bags requires notification of the treatment assignment 1 business day prior to administration in order to prepare the infusion bag. Therefore, participants must be consented and randomized at least 1 day prior to the scheduled procedure.

Baseline measures will include:

- Inclusion/Exclusion criteria assessment
- Demographics and medical history
- World Health Organization AUDIT questionnaire
- CARDIA alcohol use questionnaire (shortened version)
- Vital signs
- Infusion, procedure, BrAC, and EP study measurements
- Arrhythmia episodes pre/during/post-procedure
- Adverse event assessment

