methanol and ethylene glycol poisoning. The blood alcohol levels that have been used in such situations (0.1 to 0.2%) are higher than the level that we will use in our study (0.08%). Side effects from the ethanol infusion at our targeted dose may include mild headache, but it is unlikely to cause nausea and vomiting. Early studies with high dose IV ethanol infusions used for surgical anesthesia in the 1960s targeted to blood ethanol concentrations of 0.2 to 0.4% resulted in dizziness, nausea and/or vomiting. Most of these symptoms resolved by 24 hours. In more recent experiments using the moderate levels of ethanol that we will target (0.08% blood alcohol concentration), only mild headache, with no nausea or vomiting, has been reported. There have been no reports of serious adverse events with IV ethanol titrated by the BrAC quick clamp method. In addition, previous studies in which oral whiskey was administered to patients undergoing invasive electrophysiology (EP) studies (discussed above) did not result in any serious adverse events. While the total volume infused in either the ethanol group or the placebo (D5 half normal saline) group is not expected to exceed 500 cc, there is the theoretical possibility of causing volume overload; of note, patients with a history of heart failure or LVEF < 50% will be excluded. It is possible that ethanol may potentiate the side effects of other sedatives in patients undergoing AF ablation procedures, but this is unlikely. All of these cases are staffed by board certified anesthesiologists (with continuous 12 lead electrocardiograms, pulse oximetry, CO2 monitoring, and blood pressure monitoring per an arterial line per standard of care) as well as a cardiac EP attending, a cardiac EP fellow (board certified or board eligible in cardiology) and two nurses. All patients have several large sheaths in place for venous access, defibrillation pads already in place, and the intracardiac catheters can provide pacing if necessary. An echocardiography machine is immediately available in the EP laboratory and at least one on call interventional cardiologist and interventional cardiology fellow are available in the cardiac catheterization laboratory in the same suite

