We observed no complications and no difficulties with recovery or wound healing in the 3 AF ablation patients receiving IV ethanol titrated to a blood ethanol concentration of 0.08% using the BrAC quick clamp method. We are not aware of any evidence to suggest that ethanol should adversely affect the efficacy of the AF ablation or the recovery or wound healing processes.

Additional risks include prolongation of the AF ablation procedure. We anticipate that the additional procedure time will average 40 minutes. The left atrial anatomic map will be created using the three dimensional mapping system per the standard clinical procedure while the ethanol or placebo infusion is started and titrated to steady state, helping to minimize any extra procedure time. This additional procedural time may minimally increase the patient's risk for stroke or sedation complications including pneumonia, deep vein thrombosis, or pulmonary embolism. Although the EP tests that will be performed and attempts to induce AF are consistent with standard of care during AF ablation procedures per the most recent expert consensus (as well as standard of clinical practice in the UCSF cardiac EP laboratory), the potential induction of AF includes a risk of cardioversion, which may minimally increase the risk of skin burns and stroke. As per standard of care, all patients may undergo transesophageal echocardiograms immediately prior to the procedure to exclude the presence of a left atrial appendage thrombus and all will receive IV heparin with serial ACT monitoring to minimize the risk of stroke.

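### The Table 2 footnote sets a minimum age for the screening echocardiogram and no maximum, which conflicts with the screening timetable and with the purpose of the LVEF exclusion

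*Protocol*

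**What the plan says.** Table 2 (protocol Section 5.0) places the TTE in the Screening column only. Its timing footnote reads "Must be performed $\geq 1$ year prior to study procedure". No upper limit on the age of the echo appears there or elsewhere in the protocol.

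Exclusion 2 in Section 2.6.2 is an LVEF below 50%. It names no source for the value and no date by which it must have been measured. Section 6.1 relies on it when discussing the infused volume: "there is the theoretical possibility of causing volume overload; of note, patients with a history of heart failure or LVEF < 50% will be excluded".

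On screening, Section 5.1 says that each candidate's "medical record will be reviewed for available inclusion and exclusion criteria data". It also says "Initial screening will occur at least 1 day prior to the" planned ablation. The only other echocardiogram planned before the procedure is in Section 6.1, where "all patients may undergo transesophageal echocardiograms immediately prior to the procedure to exclude the presence of a left atrial appendage thrombus". That examination is optional and is not described as a check of LVEF.

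**The concern.** An exclusion based on ventricular function is meant to describe the heart at the time of the infusion. A rule on the age of the supporting echo would normally stop the value from being too old. This footnote stops it from being too recent. A site that followed it exactly could complete the schedule with an echo several years old, and could not complete it with one from last month.

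At stake is how well the LVEF exclusion works as a safety screen, and whether the protocol gives staff a rule they can sensibly follow and be audited against.

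**Working it through.** No sample size, power or alpha figure enters this point, so the check is a comparison of texts.

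**Step 1: which row the footnote belongs to.** The markers do not match: an asterisk on the row label, a 1 in the cell and a dagger on the footnote. However, the TTE cell is the only cell in Table 2 with a superscript, and this is the only footnote giving a timing rule for an evaluation. It can only belong to the TTE.

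**Step 2: what the inequality means.** The footnote requires echo age ≥ 1 year on the day of the procedure. An echo from 1 day to just under 1 year old fails. One that is 1 year old, 5 years old or older passes.

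**Step 3: against the screening timetable.** Table 2 lists the TTE as a screening evaluation, and Section 5.1 allows screening as late as 1 day before the procedure. A TTE done at such a visit is 1 day old and cannot satisfy the footnote. Only an echo already in the chart for a year can.

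**Step 4: against the exclusion.** Taking the footnote with exclusion 2, the chart review in Section 5.1, and Section 4.1 (no infusion if an exclusion comes to light before or at the start of the procedure):

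| Echoes in the chart | Footnote met? | Exclusion 2 | Result |
|---|---|---|---|
| Recent only, LVEF 50% or more | No | Not met | Eligible, but off schedule |
| Recent only, LVEF below 50% | No | Met | Excluded |
| Old LVEF 50% or more, recent LVEF below 50% | Yes, by the old one | Met, by the recent one | Excluded |
| Old only, LVEF below 50% | Yes | Met | Excluded |
| Old only, LVEF 50% or more | Yes | Not met on the value held | Eligible; current LVEF unknown |

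The first row is a departure from Table 2, and Section 8.0 requires every deviation to be reported. The last row is the gap in the safety screen, because nothing in the protocol calls for a current value.

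**Step 5: how much rests on the exclusion.** Section 6.1 says "patients with a history of heart failure or LVEF < 50% will be excluded". Of those two grounds, only LVEF is among the nine exclusions in Section 2.6.2; a history of heart failure is not listed. The TTE is also the only scheduled evaluation that would supply an LVEF. The footnote therefore governs the one scheduled measurement behind the one listed criterion.

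**The case against.** The strongest reply is that the footnote decides only whether a scheduled evaluation counts as done. Exclusion 2 stands on its own, chart review takes in whatever is available, and Section 4.1 gives a last check. This is right. A reader might infer that the protocol would have staff set aside last month's LVEF of 40% in favour of a three-year-old 60%. The documents do not require that, and such a patient would be excluded.

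A second reply is that the sign is a slip, or was misread when the text was taken from the PDF. Either is possible, and the mismatched footnote markers are a reason to look at the original page. If the page shows the same sign, a drafting inversion is the likeliest explanation, but the table still states the rule against which deviations are judged.

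Third, Section 5.0 leaves full timing details to the Operations Manual, which is not among the documents. This limits what can be said about actual practice. It does not cure the table, since a manual should not have to contradict the protocol.

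Fourth, Section 6.1 calls volume overload theoretical, does not expect the infused volume to exceed 500 cc, and describes close monitoring with an echo machine in the laboratory. This lowers the clinical stakes and leaves the inconsistency where it is.

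Finally, the SAP, dated 12/7/2020, describes the analyses in the past tense, so enrolment appears to be over. The text correction would then change no eligibility decision, and the retrospective check becomes the useful part.

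**Conclusion.** The footnote is wrong as it stands. It sets a minimum echo age of 1 year with no maximum, it cannot be met by a TTE done at a screening visit shortly before the procedure, and it works against the purpose of the LVEF exclusion.

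The consequences are narrow. They are (a) a participant whose only LVEF is a year old or more, with no current value required, and (b) a participant with only a recent echo, who is technically off schedule. The rule applies to all 100 planned participants, but the number in either group cannot be derived. The documents give neither the ages of the echoes nor a rate at which LVEF falls below 50%.

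A reader might go further and infer that a predictable number of ineligible patients was infused, or that undetected ventricular dysfunction altered atrial refractoriness or AF inducibility. The documents support neither inference. Power, alpha and the primary analysis are not affected.

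The conclusion assumes that the symbol was read correctly from the original page, and that the screening TTE is the expected source of LVEF. The protocol implies the second but does not state it.

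**What to change.** 1. Check the symbol against the original page of Table 2. If the page limits the age of the echo instead, only the footnote markers need correcting.
2. If the symbol stands, reconcile the footnote with exclusion 2 and Sections 5.1 and 6.1, so that it limits how old the echo may be. A window of within 1 year was apparently meant; the sponsor should confirm this.
3. State that exclusion 2 is judged on the most recent LVEF available before randomization.
4. For participants already enrolled, list the date and value of the LVEF used for eligibility, compare it with any later value obtained before the procedure, and log any below 50%.

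The text change is one symbol, one sentence and consistent footnote markers. In any further enrolment, a few patients with only an old echo would need a current one. The retrospective check is a chart review of at most the 100 planned participants.
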